#### **9.4 Frequency of data collection**

All data collection will begin immediately upon enrollment. Study accrual, subject retention, subject adherence to intervention sessions, and study safety will be reviewed by the DSMB every 6 months (and more frequently if needed) starting 6 months after randomization of the first cohort. The PHQ-9 will be administered at the baseline study visit, 2-month study visit, and 6-month study visit to screen for depression and suicide. The Stress Experience Survey which includes questions about the most common meditation-related symptoms and other stress-related symptoms, will be administered by the research coordinator at the baseline study visit, follow-up phone call after Class #4, 2-month study visit, and 6-month study visit. Additionally, to allow for corrective feedback during the MBSR course, subjects will be sent a link from REDCap to complete a Midway Check-in questionnaire after Class #5 so that instructors can adjust mindfulness practice recommendations when indicated based on subjects' responses. The research coordinator will also administer a Hypoglycemia Survey at the baseline study visit, follow-up phone call after Class #4, 2-month study visit, and 6-month study visit. See Data and Safety Monitoring Plan in Appendix.

#### **9.5 Individuals reviewing the data**

See Data and Safety Monitoring Plan in Appendix.

#### **9.6 Frequency of review of cumulative data**

See Data and Safety Monitoring Plan in Appendix.

#### **9.7 Statistical tests**

Not applicable

#### **9.8 Suspension of research**

This study will be stopped prior to its completion if: (1) the intervention is associated with adverse effects that call into question the safety of the intervention; (2) difficulty in study recruitment or retention will significantly impact the ability to evaluate the study endpoints; (3) any new information becomes available during the trial that necessitates stopping the trial; or (4) other situations occur that might warrant stopping the trial.

The PI will include an assessment of futility in the annual progress report to NIH and will consult with the study monitors and the NIH Program Official to assess the impact of significant data loss due to problems in recruitment, retention, or data collection.

## **10.0 Risks**

### Risks of Stress Reduction Programs

*Meditation-related risks:* NCCIH states that meditation is generally safe for healthy people, but that adverse effects have also been reported (NCCIH, 2018). Undesirable side effects and risks of meditation have been

documented in more than 40 scientific reports [for reviews see (Lindahl et al., 2017; Lustyk et al. 2009; Kuijpers et al., 2007; Baer et al, 2019; Britton, 2019; Van Dam et al., 2018)] and are listed in Mindfulness-Based Program Guidelines (Kuyken et al., 2012; Santorelli et al., 2017). More common, less serious side effects that have been reported by individuals within the context of mindfulness-based interventions (MBIs) or who are meditating less than an hour of daily practice include: increased depression, anxiety or panic, re-experiencing of traumatic memories, dissociation, executive dysfunction, headaches/body pain and insomnia (Lindahl et al., 2017; Lomas et al., 2014; Cebolla et al., 2014; Brooker et al., 2013; Johnson et al., 2016; Reynolds et al., 2017; Britton et al., 2010). A few case reports of more serious side effects including mania, psychosis, and suicidality have been reported, mostly in the contexts of intensive retreats (>5 hrs/day) or in conjunction with pre-existing psychopathology (Lindahl et al., 2017; Kuijpers et al., 2007; Kuyken et al., 2012; Yorston, 2001). The frequency of serious adverse effects in the context of MBIs is estimated to be less than 1%, although adequate estimates are not available (Wong et al., 2018). The frequency of non-serious Adverse Events with mild-moderate impairment in functioning is unknown; available estimates range from 1-25% (Baer et al., 2019).

To minimize this risk, we will monitor subjects' levels of distress during the study and use trained instructors who are experienced in detecting when participants of their MBSR class are experiencing increased distress and then providing appropriate corrective feedback e.g. adjustment of MBSR practice, referral to a mental health specialist, etc. Subjects will be monitored for the most common meditation-related symptoms and other stress-related symptoms with the Stress Experience Survey at the baseline study visit, follow-up phone call after Class #4, 2-month study visit, and 6-month study visit. Additionally, subjects will be monitored at each study visit for worsening depressive symptoms and suicidal thinking using the Patient Health Questionnaire-9 (PHQ-9). Subjects with suicidal ideation will be referred to one of the following appropriate resources for immediate evaluation:

1. [name] (cell [contact])
2. [name] ([name], cell [contact])
3. Psychiatric consult

Additional resources for meditation-related adverse effects, including dissociation:

- The study MBSR instructors [name] and [name]
- Co-Investigators [name] and [name]
- External consultant [name]

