**Other study procedures the SME instructor will complete:**

Once an SME instructor randomizes a subject to MBSR or SME, that SME instructor will be responsible for following that subject throughout the time that the subject is in the study, and completing any study procedures that cannot be completed by the blinded research coordinators, including:

- By Class #1, record the number of subjects in their cohort randomized to each group (and any other needed information) in the Unblinded Classes sheet in the Excel Study Tracking Spreadsheet in Google Drive. This information will be used by unblinded research team members e.g. the SME instructors, to check that the correct number of subjects started up the MBSR and SME Daily Diary surveys after Class #1. Blinded study team members cannot be aware of the number randomized to each group in a cohort since this could reveal group assignments.
- Coordinate the documentation of attendance at the MBSR or SME sessions for each subject in their cohort (See the section below entitled “Attendance”)
- To encourage subject retention in the study, and to parallel what is commonly done in MBSR, after Class #8, the instructors will invite the subjects to participate in additional MBSR or SME Retreat sessions and monthly booster sessions (See SME Instructor Email Template After Class #8 MBSR Booster Reminder and SME Instructor Email Template After Class #8 SME Booster Reminder). The monthly booster sessions in months 3 to 6 are required sessions for the study. The remaining booster sessions, and any additional Retreat sessions after Class #8, are optional. Attendance will be recorded at these additional sessions, however subjects will not receive any financial compensation for participating in the optional sessions.
- The SME instructor will serve as the point-of-contact for any and all communications between the MBSR/SME instructors and the blinded research team about subjects in a manner that does not reveal a subject’s group assignment (See the section below entitled “Blinding”).
- A subject’s SME instructor will be the one main point person that the subject can contact with any questions about the study. This will be very important in building rapport with the subject and encouraging retention in the study.
- Any other study procedures that cannot be completed by the blinded research coordinators.

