**Outline of MBSR Booster Sessions:**

- Minutes 1 to 10 - Socializing
- Minutes 11 to 20 - Didactic on topic based on MBSR (Instructors will keep a log of topics discussed with dates)
- Minutes 21 to 35 - Mindfulness practice
- Minutes 36 to 45 - Discussion regarding practice

**Stress Management Education (SME) control group:** Subjects randomized to the SME control group will receive [name] Stress Management Education (SME) program, adapted for live online delivery due to the COVID-19 pandemic. Stress Management Education was specifically created as a control condition for MBSR studies so it matches MBSR for time, social support, homework, etc. (Hoge et al., 2013). Stress Management Education does not have any mindfulness in it. The instructors for the SME sessions will have prior experience working with groups and they will be trained by [name] to teach SME in the study. [name] will continue to be available throughout the study in case any questions arise about SME. The SME program includes nutrition (which will be adapted for the diabetes population), exercise as gentle stretching with Theraband to match yoga in MBSR, and other general health topics that may be relevant to the diabetes population such as sleep, time management, etc. Homework for the SME control group will be excerpts of audiobooks about general stress management or nutrition facts. The SME control group will follow a manualized intervention, be optimized in its appeal to subjects, and have regular supervision and facilitator buy-in just like the MBSR group, as is recommended for active controls for MBSR studies (MacCoon et al., 2012). The SME control group will not involve any mindfulness.

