### **8.2 Sample size determination**

The primary outcome for this trial is the absolute difference between the two interventions with respect to the mean change in hemoglobin A1c from baseline to month 6 and we consider an absolute difference of 0.5% in this outcome to be clinically meaningful. As this is an individually randomized group treatment trial, correlation among observations within groups (defined here as class cohort), as measured by the intraclass correlation coefficient (ICC), must be taken into consideration (Pals et al., 2008). The variance inflation factor, or design effect, for this type of trial will inflate the sample size by  $1+(1-m)p$ , where  $m$  is the average group size and  $p$  is estimated by the ICC. For both interventions (MSBR and SME), we plan to have the average group size be 18 subjects and expect the ICC=0.08. Thus, the design effect is 2.36. Furthermore, we anticipate that 15% of the subjects will drop-out of the study prior to completion. Incorporating the design effect of 2.36 and the anticipated 15% drop-out, a sample size of 290 subjects (145/intervention) will provide 80% power to detect a clinically meaningful 0.5% absolute difference between the two interventions with respect to the mean change in hemoglobin A1c from baseline to month 6, assuming a standard deviation of 0.9% (Frias et al., 2011) using a two-sided test having a significance level of 0.05.

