Adverse events will be recorded at each study visit (the baseline study visit, follow-up phone call after Class #4, 2-month study visit, and 6-month study visit) and throughout the study whenever subjects or their instructors initiate reporting of an adverse event. Within 24 hours, adverse events in participants assigned to MBSR will be reported via phone or email by [name] from West Chester University (or other study MBSR instructor e.g. [name]) to the SME instructors to maintain blinding. Within 24 hours, adverse events in all participants (MBSR and SME) will be reported via phone or email by the SME instructor to the blinded research coordinator and the overall study PI [name] at the primary site at Hershey. The SME instructor will communicate adverse events (e.g. requiring a change in MBSR or SME practice recommendations), and other information about MBSR subjects and SME subjects, to the blinded research coordinator and to [name] in a manner that does not reveal which instructor the subject reported the adverse event to, or any other information that would reveal the subject's group assignment. To accomplish this, we will minimize the 'discussion' aspect of how the SME instructors report the AE, or any other information about a subject, to the research coordinator because discussion of the report may lead to unblinding/may make it obvious as to which instructor it was reported to if the SME instructor doesn't know much about the encounter. The SME instructor will simply state e.g. "Participant ID 123 has reported  to an instructor." The research coordinator will then follow up with the subject via phone for formal AE documentation. If indicated, the research coordinator will complete an Adverse Event form.

All subjects will be followed up to 6 months. Adverse events will be followed for outcome information until resolution or stabilization. Adverse events will also be entered in the REDCap database.

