The Stress Experience Survey will be administered by the research coordinator at the baseline study visit, follow-up phone call after Class #4, 2-month study visit, and 6-month study visit. This includes questions about the most common meditation-related symptoms (items 1 to 10) and a question about other stress-related symptoms. This survey was adapted from [name] MBP-Specific Adverse Effects Survey (Britton\_Version9.18.19), which represents the 10 most common meditation-related symptoms from the Varieties of Contemplative Experience Phenomenology Codebook (Lindahl et al., 2017), as replicated in an NIH-funded mindfulness-based intervention clinical trial (Britton, in prep).

Additionally to allow for corrective feedback during MBSR, subjects will be sent a link from REDCap to complete a Midway Check-in questionnaire after Class #5 so that instructors can adjust mindfulness practice recommendations when indicated based on subjects' responses. The study

MBSR instructors have been provided with resources to supplement their teacher training with meditation safety and trauma informed mindfulness, including the Meditation Safety Toolbox (<https://www.brown.edu/research/labs/britton/resources/meditation-safety-toolbox>) and Trauma-Sensitive Mindfulness (<https://davidtreleaven.com/>).

At each study visit subjects will be screened for depressive symptoms and suicidal thinking using the Patient Health Questionnaire-9 (PHQ-9). The PHQ-9 will be self-administered in REDCap at the screening visit, baseline visit, 2-month visit, and 6-month visit. At every study visit, the blinded research coordinator will review the subjects' responses to the PHQ-9 in REDCap. If any answers are missing, the research coordinator will ask the subject: "Are you sure you meant to skip this question?" If the subject did not mean to skip the question, the research coordinator will be able to go in and enter the subject's response (REDCap will track that the research coordinator entered the response).

If a subject is not comfortable with answering the 9th item of the PHQ-9 at the screening visit, they will be excluded from the study. If a subject refuses to answer the 9th item of the PHQ-9 at any of the subsequent study visits, the subject will be excluded from the study, and the research coordinator will immediately contact one of the below suicidality experts.

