### E.3 Other Measures for Monitoring AEs

**E.3.1 Stress Experience Survey [Adapted from [name] program-specific adverse effects (MBP-SPEC-AE) survey].** CONSORT-Harms guidelines (Ioannidis et al., 2004) recommend using standardized and validated scales that assess treatment-specific symptoms, because they have more accurate detection rates than passive monitoring (Stephens et al., 1998) or open-ended queries (Wallin and Sjovall, 1981; Bent et al., 2006) and are low cost, low burden and require no special training to administer.

To accommodate these recommendations, and to create a systematic query of treatment-specific symptoms in all treatment arms, the research coordinator will administer the Stress Experience Survey to specifically query the most common meditation-related side effects (anxiety, depression, dissociation, re-experiencing of traumatic memories etc.) found in 8-week MBIs using patient-reported outcomes measurement information system (PROMIS) or NeuroQol items (or other validated scales if construct is not available). The Stress Experience Survey includes questions about the most common meditation-related symptoms (items 1 to 10), as well a question about other stress-related symptoms. This survey was adapted from [name] MBP-Specific Adverse Effects Survey (Britton\_Version9.18.19), which represents the 10 most common meditation-related symptoms from the Varieties of Contemplative Experience Phenomenology Codebook (Lindahl et al., 2017), as replicated in an NIH-funded mindfulness-based intervention clinical trial (Britton, in prep). Subsequently, the research coordinator will record any item occurring more frequently compared to baseline, or previous visit responses, as an Adverse Event and assess its severity (using the Severity Grading Tool in Appendix C1) and relatedness (using the Relatedness Criteria Definitions Table above in section IV-C). Subjects will be asked to provide further detail (i.e., date of onset, symptomology, circumstance surrounding the event, relatedness to the intervention, etc.) on any AE/SAE reported in the Stress Experience Survey. These details will be used to assess the need for treatment modification, referrals and reporting.

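### Spontaneously reported adverse events may be picked up more readily in the MBSR arm, and the adverse event record has no source item that would show it

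*Combined protocol and SAP*

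**What the plan says.** Adverse events reach the record by two routes.

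- **Scheduled queries.** The Stress Experience Survey, the Hypoglycemia Survey and the PHQ-9 run on the same schedule in both arms. Blinded coordinators administer the two surveys and review the PHQ-9. DSMP section IV.E.3.1 prefers such standardized scales "because they have more accurate detection rates than passive monitoring" and intends the survey for all arms.
- **Spontaneous reports.** Section 9.3 and DSMP IV.E also collect events "throughout the study whenever subjects or their instructors initiate reporting of an adverse event". Section 7.2.4 (Blinding) routes whatever an instructor becomes aware of, in either arm, through the SME instructor to the blinded coordinator.

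The instructors are described differently. Section 10.0 says the study will "use trained instructors who are experienced in detecting when participants of their MBSR class are experiencing increased distress". DSMP IV.D adds that the study "MBSR instructors have been provided with resources to supplement their teacher training with meditation safety and trauma informed mindfulness", and the MBSR part of section 7.2.4 says the same. For the comparator, section 7.2.4 says only: "The instructors for the SME sessions will have prior experience working with groups and they will be trained by" a named trainer. The roles differ too. In both arms a subject's "SME instructor will be the one main point person that the subject can contact with any questions about the study", so an MBSR subject has a class teacher as well, while in the SME arm one person can fill both roles.

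The Adverse Events Form (items a to k), the Serious Adverse Events Form (items a to p) and Tables 6 and 7 of DSMP Appendix A have no item for how an event was found.

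**The concern.** In a trial where one arm's teachers are prepared to look for distress and the other arm's are not described that way, equal true harm can produce unequal counts. The usual remedy is to know how each event came to light, so that events found by identical questioning can be compared on their own. This record does not allow that, because both routes feed one form and one table.

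The comparison is foreseeable even though none is specified. The safety plan is built on the CONSORT harms guidance. The first stopping criterion asks whether the intervention is associated with adverse effects, and DSMP III.C lets the DSMB request group-identifiable adverse event data. The background section hopes the trial will support adding MBSR to diabetes standards of care, so its harm profile will be read closely.

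The other adverse event fields do not repair this. The relatedness criteria are largely worded around meditation and the main expectedness list is of meditation effects. Neither can be applied evenly to an arm with no mindfulness content.

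**Working it through.** The documents give no figure for adverse event detection or for a between-arm harm comparison, so there is no stated result to reproduce. The arithmetic only shows how the size depends on assumptions.

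**Inputs from the documents**
- n = 145 per arm. Section 8.2: "a sample size of 290 subjects (145/intervention) will provide 80% power". This reproduces: 52 per arm (0.5 difference, SD 0.9, t-based) × 2.36 / 0.85 = 144.4, rounded up to 145. It is used here only as the arm size.
- Non-serious event frequency in mindfulness programmes: unknown, with estimates of 1 to 25% (section 10.0).

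**Assumptions, not in the documents**
- True risk p is the same in both arms.
- Spontaneous detection q for one reporter is 0.30 or 0.50. For two independent reporters it is 1 − (1 − q)²: 1 − 0.7² = 0.51 and 1 − 0.5² = 0.75.
- The scheduled queries catch a share s of events, equally in both arms.
- An unplanned two-proportion z-test at two-sided 0.05, ignoring class clustering.

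**Formula.** Observed proportion = p × [1 − (1 − s)(1 − q)].

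**Results at p = 0.30** (MBSR vs SME)

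| s | q = 0.51 vs 0.30 | ratio | q = 0.75 vs 0.50 | ratio | chance of p < 0.05 |
|---|---|---|---|---|---|
| 0 | 15.3% vs 9.0% | 1.70 | 22.5% vs 15.0% | 1.50 | about 37% |
| 0.5 | 22.7% vs 19.5% | 1.16 | 26.3% vs 22.5% | 1.17 | 10 to 12% |
| 0.8 | 27.1% vs 25.8% | 1.05 | 28.5% vs 27.0% | 1.06 | about 6% |

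Example, second row, left: 0.30 × (1 − 0.5 × 0.49) = 0.2265 and 0.30 × (1 − 0.5 × 0.70) = 0.195.

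The 30% lies above the documents' own range. At p = 0.10 and s = 0.5 the last column falls to about 6%.

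**Sensitivity within the documents' range.** Take p = 0.25, q = 0.30 in SME and double that in MBSR. The ratio is 2.00, 1.23 or 1.07 for s = 0, 0.5 or 0.8. The expected spurious excess in 145 MBSR subjects is 10.9, 5.4 or 2.2 events. The chance of a nominally significant MBSR excess is 53%, 13% or 5%, against 2.5% with no bias. If the design effect planned for HbA1c, 1 + (18 − 1) × 0.08 = 2.36, also applied to adverse events, it would be 26%, 8% or 4%. At p = 0.01 the excess is below half an event throughout. If detection is equal there is no excess.

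**The case against.** Several points on the other side stand.

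- **No planned test is affected.** Section 8.3 specifies no between-arm adverse event analysis, section 9.7 is marked not applicable, and DSMB tables are aggregate. The significance test above is an illustration only.
- **Much of the system is symmetric.** All subjects are invited to report to instructors or study staff (DSMP IV.E.3.3). Both arms receive a Midway Check-in form, session numbers are matched, and missed-session contact is similar. The coordinator follows up every relayed report by phone.
- **The section 10.0 sentence is about reducing risk, not finding events.** That is so, but the relay rule turns what an instructor notices into a possible adverse event.

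A reader might infer three stronger things that the documents do not support.

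- **That MBSR will show excess harm with no true difference.** The documents show an opportunity for bias, not its certainty or size. MBSR reports pass through an extra relay step, which could push the other way.
- **That an MBSR subject has two independent reporters and an SME subject one.** The SME instructor is also the relay for the MBSR teacher, unblinded coordinators share phone contact in both arms, and every subject can reach study staff. The 1 − (1 − q)² figures are therefore illustrative, and a false-positive rate near 37% also needs the surveys to catch nothing.
- **That nothing can be separated later.** DSMP IV.E.3.1 defines a survey-detected event as an item more frequent than at baseline or the previous visit, so a survey-based comparison can be rebuilt from the responses. The spontaneous part of the adverse event record cannot be isolated: the instructors' contact logs cover only missed sessions.

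**Conclusion.** The concern holds as a risk of differential ascertainment. The documents establish that distress-detection experience and safety resources are stated for MBSR instructors only, that MBSR subjects have a separate class teacher as well as the shared point person, and that the record has no source item. A by-arm count of all adverse events could be biased, probably against MBSR, and the record as planned would not show by how much.

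The size rests on assumed detection rates and on how much the scheduled queries catch. It ranges from substantial if they catch nothing to slight if they catch 80%, and it shrinks further at lower true risk. The primary HbA1c analysis is untouched. The change is worth making because it is cheap and reduces bias in any by-arm harms report.

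**What to change.** 1. Add a source item to the Adverse Events Form, the Serious Adverse Events Form and Tables 6 and 7: scheduled survey, PHQ-9, instructor (without saying which), subject, attrition. Allow more than one source, so that an event an instructor reports first and a survey also finds still counts as survey-found. This is safe for blinding: the scripted relay already tells the coordinator that a report came through an instructor, and only which instructor is withheld.
2. State that any between-arm harm comparison will rest on events found by the identical scheduled queries, with all spontaneous events reported separately by arm.
3. Give SME instructors written guidance, equivalent to what MBSR instructors have but free of mindfulness content, on noticing and reporting distress.

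The cost is one form field, one table column and adapting existing guidance, with no extra visits or staff. The small downside is that the main harm comparison leaves out spontaneous events, which are still listed in full. For events already recorded, survey-based counts can be rebuilt from the stored responses.
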